**TABLE 9.1.2 SHIFT CHANGES OF MOBILITY DIMENSION OF EQ-5D-5L BASED ON [REDACTED]**

**TABLE 9.1.3 SHIFT CHANGES OF MOBILITY DIMENSION OF EQ-5D-5L BASED ON [REDACTED]**

**TABLE 9.2.1 SHIFT CHANGES OF SELF-CARE DIMENSION OF EQ-5D-5L BASED ON OBSERVED DATA.**

**TABLE 9.2.2 SHIFT CHANGES OF SELF-CARE DIMENSION OF EQ-5D-5L BASED ON [REDACTED]**

**TABLE 9.2.3 SHIFT CHANGES OF SELF-CARE DIMENSION OF EQ-5D-5L BASED ON [REDACTED]**

**TABLE 9.3.1 SHIFT CHANGES OF USUAL ACTIVITIES DIMENSION OF EQ-5D-5L BASED ON OBSERVED DATA.**

**TABLE 9.3.2 SHIFT CHANGES OF USUAL ACTIVITIES DIMENSION OF EQ-5D-5L BASED ON [REDACTED]**

**TABLE 9.3.3 SHIFT CHANGES OF USUAL ACTIVITIES DIMENSION OF EQ-5D-5L BASED ON [REDACTED]**

**TABLE 9.4.1 SHIFT CHANGES OF PAIN/DISCOMFORT DIMENSION OF EQ-5D-5L BASED ON OBSERVED DATA.**

**TABLE 9.4.2 SHIFT CHANGES OF PAIN/DISCOMFORT DIMENSION OF EQ-5D-5L BASED ON [REDACTED]**

**TABLE 9.4.3 SHIFT CHANGES OF PAIN/DISCOMFORT DIMENSION OF EQ-5D-5L BASED ON [REDACTED]**

**TABLE 9.5.1 SHIFT CHANGES OF ANXIETY/DISPERSION DIMENSION OF EQ-5D-5L BASED ON OBSERVED DATA.**

**TABLE 9.5.2 SHIFT CHANGES OF ANXIETY/DISPERSION DIMENSION OF EQ-5D-5L BASED ON [REDACTED]**

**TABLE 9.5.3 SHIFT CHANGES OF ANXIETY/DISPERSION DIMENSION OF EQ-5D-5L BASED ON [REDACTED]**

Same shells as 9.1.1

**TABLE 9.6.1.1 CHANGE FROM BASELINE ON THE MOBILITY DIMENSION DURING THE TRIAL BASED ON [REDACTED]**

Visit	OR of improvement	95%CI for OR
Month 3		
Covariate 1...n		

Footnote: adjusted for covariates OR: Odds Ratio

**TABLE 9.6.1.2 CHANGE FROM BASELINE ON THE MOBILITY DIMENSION  
DURING THE TRIAL BASED ON [REDACTED]**

**TABLE 9.6.2.1 CHANGE FROM BASELINE ON THE SELF-CARE DIMENSION  
DURING THE TRIAL BASED ON [REDACTED]**

**TABLE 9.6.2.2 CHANGE FROM BASELINE ON THE SELF-CARE DIMENSION  
DURING THE TRIAL BASED ON [REDACTED]**

**TABLE 9.6.3.1 CHANGE FROM BASELINE ON THE USUAL ACTIVITIES  
DIMENSION DURING THE TRIAL BASED ON [REDACTED]**

**TABLE 9.6.3.2 CHANGE FROM BASELINE ON THE USUAL ACTIVITIES  
DIMENSION DURING THE TRIAL BASED ON [REDACTED]**

**TABLE 9.6.4.1 CHANGE FROM BASELINE ON THE PAIN/DISCOMFORT  
DIMENSION DURING THE TRIAL BASED ON [REDACTED]**

**TABLE 9.6.4.2 CHANGE FROM BASELINE ON THE PAIN/DISCOMFORT  
DIMENSION DURING THE TRIAL BASED ON [REDACTED]**

**TABLE 9.6.5.1 CHANGE FROM BASELINE ON THE ANXIETY/DEPRESSION  
DIMENSION DURING THE TRIAL BASED ON [REDACTED]**

**TABLE 9.6.5.2 CHANGE FROM BASELINE ON THE ANXIETY/DEPRESSION  
DIMENSION DURING THE TRIAL BASED ON [REDACTED]**

Same shells as 9.6.1.1

**TABLE 10.1.1 SUMMARIES OF SMAQ QUESTIONNAIRE BASED ON OBSERVED  
DATA.**

N=xxx

Forget to take the medication for IPF

Yes

No

Missing

Always take your medication for IPF at the indicated time.

Yes

No

Missing

If feel worse, do you stop taking the medication for IPF?

Yes

No

Missing

At the last week, How often did you miss the medication for IPF?

Never

1-2 times

3-5 times

6-10 times

More than 10 times

At the past 3 Months

N=xxx

Days of missed medication for IPF

n  
 Mean  
 Median  
 SD  
 Minimum  
 Maximum  
 Q1  
 Q3  
 Missing

Days of missed one of the two daily doses of medication for IPF

n  
 Mean  
 Median  
 SD  
 Minimum  
 Maximum  
 Q1  
 Q3  
 Missing

**TABLE 10.1.2 SUMMARIES OF SMAQ QUESTIONNAIRE BASED ON [REDACTED]**

Same Shell as 10.1.1

**TABLE 10.2.1 PROPORTION OF ADHERED AND NOT ADHERED PATIENTS BASED ON OBSERVED DATA.**

Adherence	n	%
Yes		
No		
Missing		

\*EQ-VAS: EQ visual analogue scale.

**TABLE 10.2.2 PROPORTION OF ADHERED AND NOT ADHERED PATIENTS BASED ON [REDACTED]**

Same shell as Table 10.2.1

**TABLE 10.2.3 CHANGE FROM BASELINE OF CAT SCORE BY ADHERENCE**

Adherence	n	Mean	Median	SD	Min	Max	Q1	Q3	Missing	Sig.
Yes										
No										
Difference										

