9.5 STUDY SAMPLE SIZE

The sample size determination is not based on a power calculation because no hypotheses will be tested. The primary endpoint of change in score of COPD Assessment Test (CAT) within three months after the switch from Spiriva® Handihaler® to Spiolto® Respimat® will be analysed descriptively by mean and 95% confidence interval. From other studies a mean difference in CAT score of 1.0 and standard deviation of 9.0 are expected.

With a sample size of 1310, a two-sided 95% confidence interval for the difference in paired mean scores will have an interval that extends by no more than 0.5 from the observed difference in means (e.g. an interval from 0.5 to 1.5 for a difference of 1.0), with 90% coverage probability, assuming that the true standard deviation of differences is 9.0 and that the confidence interval is based on the t statistic. The calculation was performed using the MOC3 routine from commercial software nQuery Advisor® 7.0 (██████████ [R15-1331]). To account for a 15% dropout rate, 1507 patients will be needed. Therefore, it was decided to enroll 1500 patients in the study.

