Selection bias could occur at the site level and the patient level. Therefore, to reduce the site level selection bias, the goal is to have participating pulmonologists/centers that have access to all available treatment options, which are approved for use in Greece for the targeted COPD patients. Information bias will be minimized by the use of standard eCRF, questionnaire and physicians' training on the study protocol.

There is also a risk of limited internal validity due to the absence of a control group. This could lead to overestimation of drug effect due to the "regression to the mean" effect sometimes observed in patients with already impaired clinical status. However, the requirement of a minimum exposure period with the previous treatment and the collection of exacerbations during the previous 12 months can help discussing from a clinical point of view any change observed during the follow-up period. Additionally, the use of different tools and scales for the measurements of clinical outcomes provides additional validation to the study, if results are consistent among them.

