### **5. AMENDMENTS AND UPDATES**

#### **5.1 Changes from protocol analysis**

Additional modifications from the CTP made in this SEAP:

- It was stated in CTP to exclude patients with missing values. Missing values will be treated in a different way according to their nature. Missing values due to Intercurrent Event (IE) are taken care at the estimands definitions, on the other hand, missing values not related to IE will be multiple imputed if missingness is greater than 25% for a specific variable.
- It was suggested in the CTP, [REDACTED]  
[REDACTED]
- To assess the potential associations between patient characteristics, treatment, preference [REDACTED]ing

to health status assessed with CAT will not be assessed via univariate methods, however the applicable [REDACTED] are included to the statistical models in the primary and the first secondary endpoint analysis.

[REDACTED]

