## 9. DATA SOURCES

Patient [REDACTED] records (paper and/or electronically) and patient reported outcomes from COPD patients as documented by the treating physician in his/her daily practice will be used as data source.

All participating physicians will be obliged to make a note of the patient's participation in the NIS in the patient 's medical records.

In the event of possible queries, the participating physician must be able to identify the patient observed. Medical information on the patient must be communicated and analyzed only using the patient number.

During this study, the following must be completed: To be completed by the physician:

- [REDACTED] (only at Visit 1)
- Patient medical files (including comorbidities and concomitant medications)
- Assessment of inhaler handling in daily use (only at Visit 2)

To be completed by the patient at Visit 1 (baseline) and Visit 2 (3-months visit):

- COPD Assessment Test (CAT)
- EQ-5D-5L questionnaire
- Modified Medical Research Council (mMRC) questionnaire

To be completed by the patient only at Visit 2 (3-months visit):

- Simplified Medication Adherence Questionnaire (SMAQ)
- Abbreviated Patient Satisfaction Questionnaire (PASAPQ)

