#### 11.2.1 Analysis of primary outcome.

11.2.1.1 Mean change in patients' quality of life (QoL) according to the total score of COPD Assessment Test (CAT) within three months after the switch from Spiriva® Handihaler® to Spiolto® Respimat®.

The primary estimand is defined as follows:

- A. Population: Is defined through inclusion/exclusion criteria of the study protocol to reflect the target population.
- B. Variable: Continuous variable response.

- C. Intercurrent Event (IE): Include death, drop-out due to any adverse event (AE) and treatment discontinuation. For patients experiencing an IE, the most extreme unfavourable value will be assigned (CAT score at 3 Months equals to 40).
- D. Population level summary: The change from Baseline of total CAT score within 3 Months.

Mixed model for repeated measurements (MMRM) assuming random missingness will be fitted. The dependent variable will be the CAT score at each visit. Visit, GOLD group, smoking habits, packyears, sex, age, and comorbidities appearing at a rate greater than 5% will be entered as covariates. Patients will be fitted at random and an unstructured covariance matrix will be used, allowing adjustment for correlations between study visits within the study patients. The Kenward- Roger degrees of freedom approximation will be used in the model (ddfm=kr).

Summaries of the estimated mean change from baseline of CAT score at 3 Months will be provided with 95% confidence interval. Model information will be provided as footnote under the corresponding table.

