**TABLE 6.2.1 CHANGE FROM BASELINE TOTAL CAT SCORE ESTIMATES DURING THE TRIAL BASED ON [REDACTED]**

Visit	LS Mean	95%CI
Month 3 Change from Baseline		
Covariate 1...n		

Footnote: CAT: COPD Assessment Test. LS: Least Square

Footnote: adjusted for covariates

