**TABLE 10.2.3 CORRELATION OF CAT CHANGE FROM BASELINE WITH WILLINGNESS TO CONTINUE WITH THE INHALER**

	R correlation	Sig.
CAT change from baseline	Willingness to continue	

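### The visible shell for CAT change by adherence compares raw change with a significance column and leaves out baseline CAT; a baseline-adjusted difference beside it would be a cheap improvement

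*SAP*

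**What the plan says.** Two shells in SAP Annex 1 relate CAT change to another patient-level variable, and both are numbered 10.2.3.

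- The first, "CHANGE FROM BASELINE OF CAT SCORE BY ADHERENCE", has rows for adherent, non-adherent and difference. Its columns are n, mean, median, SD, range, quartiles and missing, plus one headed 'Sig.'.
- The second, "CORRELATION OF CAT CHANGE FROM BASELINE WITH WILLINGNESS TO CONTINUE WITH THE INHALER", has only a correlation and a 'Sig.' column.

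Neither shows baseline CAT, a least-squares mean or a confidence interval. Neither carries the note "Footnote: adjusted for covariates" that appears under Table 6.2.1 and the other model-based tables.

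SAP section 9 lists the CAT for both visits, but the adherence (SMAQ) and satisfaction (PASAPQ) questionnaires for Visit 2 only. The primary model in SAP 11.2.1.1 does not contain adherence or willingness: "Visit, GOLD group, smoking habits, packyears, sex, age, and comorbidities appearing at a rate greater than 5% will be entered as covariates". SAP 11.2.2.4 and 11.2.2.8 plan frequency tables and summary statistics for these two outcomes and do not link them to CAT. On testing, Protocol 9.5 says: "The sample size determination is not based on a power calculation because no hypotheses will be tested".

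**The concern.** Adherence is reported by the patient at Visit 2 and is not assigned, so adherent and non-adherent patients may have started with different CAT scores. Unless the two visits are perfectly correlated, patients who start higher tend to fall more. A gap in starting severity can therefore show up as a difference in change, and the table would attach a p-value to it. The reverse can also happen: a real association can be masked. Leaving out a covariate related to the outcome also makes the comparison less precise than the collected data allow.

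At stake is how a supporting table is read. A significant result could be taken as evidence that adherence goes with greater benefit when it partly reflects where patients began.

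**Working it through.** **Inputs from the documents (Protocol 9.5).** SD of CAT change 9.0; expected mean change 1.0; planned 1310 evaluable; dropout 15%; 1500 enrolled.

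**The plan's own figure.** The smallest n for which a two-sided 95% t-interval has half-width at most 0.5 with probability 0.90 at SD 9.0 is 1310 (probability 0.9007), so 1310 reproduces. The adherence and willingness tables have no sample size or target difference of their own.

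**Assumptions, not in the documents.** Equal SDs at both visits; baseline-to-month-3 correlation rho 0.5 (range 0.3 to 0.7); baseline gap d of 1 or 2 points; equal adherence groups; evaluable N = 1500 x 0.85 = 1275, or 637.5 per group.

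**Spurious difference.** If adherence is unrelated to month-3 CAT given baseline, the expected difference in raw change has size (1-rho)d. The standard error of the raw difference is 9.0 x sqrt(2/637.5) = 0.504. At rho 0.5 and d = 2 the difference is 0.5 x 2 = 1.0 point, equal to the whole mean change the protocol expects. Then 1.0/0.504 = 1.98, which is significant at two-sided 5% in about 51% of studies.

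| rho | difference, d = 1 | significant | difference, d = 2 | significant |
|---|---|---|---|---|
| 0.3 | 0.7 | 28% | 1.4 | 79% |
| 0.5 | 0.5 | 17% | 1.0 | 51% |
| 0.7 | 0.3 | 9% | 0.6 | 22% |

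Unequal groups reduce these figures. With N = 1310, rho 0.5 and d = 2, the rate is 52% at 50:50, 45% at 70:30 and 23% at 90:10. A simulation of the 70:30 case (1500 runs) gave an unadjusted difference of size 1.03, significant in 46% of runs. After adjustment for baseline the size was 0.02, significant in 4.4%.

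**Precision.** The visit SD is s = 9/sqrt(2(1-rho)), and the residual SD after adjustment is s x sqrt(1-rho^2). This gives 7.26, 7.79 and 8.30 at rho 0.3, 0.5 and 0.7. The variance ratio of adjusted to raw is (1+rho)/2 = 0.65, 0.75 and 0.85, a cut of 35%, 25% and 15%. At rho 0.5 the 95% CI half-width falls from 1.96 x 0.504 = 0.99 to 1.96 x 7.79 x sqrt(2/637.5) = 0.86.

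**Willingness table.** If willingness correlates at r with baseline CAT and is unrelated to month-3 CAT given baseline, its correlation with change has size r x sqrt((1-rho)/2). For an assumed r of 0.2 this is 0.118, 0.100 and 0.077 at rho 0.3, 0.5 and 0.7. With N = 1310 it is significant in about 99%, 95% and 80% of studies.

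**Opposite null.** Suppose instead that the groups differ by a stable d at both visits and change equally. The raw comparison then rejects at about 5%, and the baseline-adjusted difference is off by (1-rho)d. With N = 1275 and equal groups (1500 runs), the adjusted test rejects in 22% of studies for d = 1 and 64% for d = 2 at rho 0.5. At rho 0.3 the figures are 42% and 93%; at rho 0.7 they are 10% and 26%.

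**The case against.** The strongest objection is that the bias depends on which null is true. In non-randomised groups neither raw nor adjusted change is correct by default (Lord's paradox), and the last calculation shows adjustment producing the same error under a stable-difference null. This stands. A reader might infer that the raw comparison is a demonstrated error to be replaced; the documents do not support that. They support showing both estimates and saying what each answers.

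The willingness rating is given at month 3 and may follow from improvement. Whether patients who improved more wish to continue is a fair question, and raw change answers it. A partial correlation would answer another question, so the raw r should not be removed.

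A reader might also see a contradiction with SAP 5.1, whose readable part says that associations "to health status assessed with CAT will not be assessed via univariate methods". That sentence is partly redacted and adherence is not legible in it, so no conflict is asserted. Likewise, SAP 11.3 may describe adjusted versions of these analyses. The absence of adjustment is inferred from shells that name no test.

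Protocol 9.9 raises regression to the mean for the overall change without a control group, not for a comparison of adherence groups, and so does not by itself establish the point.

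Finally, neither table is a primary or secondary outcome, and no planned power depends on them. That limits the priority. It does not remove the ambiguity of a significance column that mixes adherence with starting severity.

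**Conclusion.** The point holds as a cheap improvement to supporting tables, at low priority. On the visible shells, the adherence comparison ignores a baseline score that was measured before the adherence report. With the assumed 2-point gap, the raw difference can be 0.6 to 1.4 points over rho 0.7 to 0.3 with no conditional association, and significant in 22% to 79% of studies. Adjustment would lower the variance by 15 to 35%. These sizes rest on rho, the gap, the split and equal visit SDs, none of which the documents give.

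It would go too far to infer that the primary result is in doubt. Baseline CAT is one of the two responses in the primary repeated-measures model, so that estimate is unaffected.

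One related gap is that neither title states its data basis, although neighbouring tables do. If the intercurrent-event rules were applied, the same patients would receive CAT 40 (SAP 11.2.1.1), non-adherent status (11.2.2.4) and willingness 0 (11.2.2.8). That would build in an association which baseline adjustment cannot remove.

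**What to change.** In the adherence table:

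- Keep the raw rows and the raw difference.
- Add baseline CAT by adherence group.
- Add the adherent minus non-adherent difference from a linear model for CAT change with baseline CAT as covariate, with a 95% CI.
- If the covariates of SAP 11.2.1.1 are also entered, consider whether GOLD group is needed, since the footnote to Protocol Table 1 says it is calculated partly from CAT.
- Add a footnote that raw and adjusted differences answer different questions in non-randomised groups.

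In the willingness table, keep the raw correlation and, at most, add the baseline-adjusted slope beside it.

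In both, label 'Sig.' as exploratory, state whether observed or intercurrent-event values are used, and correct the duplicate table number.

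The cost is SAP wording, two shells and a few lines of code on data already collected. No patient is lost for want of a baseline CAT, since a change score already requires one. The downside is a little extra analysis and two estimates that may differ. The adjusted figure remains an observational association, open to other confounding and to reverse causation.

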**TABLE 11.1.1 MEAN SCORE OF PASAPQ QUESTIONNAIRE BASED ON OBSERVED DATA**

How satisfied are you with the:	n	Mean	Median	SD	Min	Max	Q1	Q3	Missing
Overall feeling of inhaling.									
Feeling that the inhaled dose goes to your lungs.									
Amount of medication left in your inhaler									
Reliability of inhaler									
Ease of inhaling a dose from the inhaler									
Instructions of use									
Size of inhaler									
Durability of inhaler									
Ease of cleaning the inhaler									
Using of inhaler									
Speed at which medicine comes out of the inhaler									
Ease of holding the inhaler during the use									
Convenience of carrying the inhaler									
Total score 1-13 Question									
Overall satisfaction of inhaler									

**TABLE 11.1.2 MEAN SCORE OF PASAPQ QUESTIONNAIRE BASED ON [REDACTED]**

Same shell as 11.1.1

**TABLE 12.2.1 PASAPQ QUESTIONNAIRE PART II BASED ON OBSERVED DATA.**

	n	%
Preference of inhaler		
Spiriva® Handihaler®		
Spiolto® Respimat®		
No preference		
Missing		
Willingness to continue using the inhaler		
n		
Mean		
Median		
SD		
Minimum		
Maximum		
Q1		
Q3		
Missing		

Footnote: Willingness' range is 0-100, where 100 indicates that the patient would definitely be willing to continue using the inhaler and 0 indicates that the patient would definitely not be willing to continue using the inhaler

**TABLE 12.2.2 PASAPQ QUESTIONNAIRE PART II BASED ON [REDACTED]**

Same shell as 12.2.1

**TABLE 10.2.3 CORRELATION OF CAT CHANGE FROM BASELINE WITH WILLINGNESS TO CONTINUE WITH THE INHALER**

	R correlation	Sig.
CAT change from baseline	Willingness to continue	

**TABLE 13.1.1 MMRC SCORE BY VISIT BASED ON OBSERVED DATA.**

Visit	n	Mean	Median	SD	Min	Max	Q1	Q3	Missing
Baseline	Base								
Month 3	Base								
	Post								
	Change								

**TABLE 13.1.2 MMRC SCORE BY VISIT BASED ON [REDACTED]****TABLE 13.1.3 MMRC SCORE BY VISIT BASED ON [REDACTED]**

Same shell as Table 13.1.1

**TABLE 13.2.1 SHIFT CHANGES OF MMRC DURING THE TRIAL BASED ON OBSERVED DATA.**

	Baseline			3 Months										
	0		1	2	3	4	Missing		Total					
mMRC Grade	n	%	n	%	n	%	n	%	n	%	n	%	n	%
0														
1														
2														
3														
4														
Missing														
Total														

**TABLE 13.2.2 SHIFT CHANGES OF MMRC DURING THE TRIAL BASED ON [REDACTED]****TABLE 13.2.3 SHIFT CHANGES OF MMRC DURING THE TRIAL BASED ON [REDACTED]**

Same shell as Table 13.2.1

[figure not shown]
**TABLE 13.3.1 CHANGE FROM BASELINE OF MMRC BASED ON [REDACTED]**

Month 3 Change from Baseline	LS Mean		95%CI	
mMRC: Modified British Medical Research Council ranged in (0-4).LS : Least Square				
Footnote: adjusted for covariates				

**TABLE 13.3.2 CHANGE FROM BASELINE OF MMRC BASED ON [REDACTED]**

**TABLE 15.1 CONTINUATION OF THERAPY**

	n	%
Continuation with Spiolto Respimat during the study		
Yes		
No		
Missing		
Reason for discontinuation		
Not work well enough		
Stopped working well		
Side effects		
Illness unrelated to treatment development		
Symptoms improved and prefer not to continue the treatment		
Too inconvenient		
Cannot afford treatment		
Other reason		
Continuation with Spiolto Respimat after the study		
Yes		
No		
Missing		

**TABLE 17.1 SMOKING STATUS CHANGES**

Has the smoking status changed from Baseline visit?	n	%
Yes		
No		
Unknown		
Missing		

**TABLE 17.2 CHANGE FROM BASELINE OF FVC (%) PREDICTED.**

Visit	n	Mean	Median	SD	Min	Max	Q1	Q3	Missing
Baseline Base									
Month 3 Base									
Post									
Change									

**TABLE 17.3 CHANGE FROM BASELINE OF FEV1/FVC (%) PREDICTED.**

**TABLE 17.4 CHANGE FROM BASELINE OF TROUGHFEV1 (%) PREDICTED.**

\*Trough FEV1 is the morning pre dose FEV1

Same shells as Table 17.2

**TABLE 17.5 SHIFT CHANGES OF PNEUMONIA**

	Baseline		3 Months						Total	
	Yes	No	Not Evaluated		Missing					
	n	%	n	%	n	%	n	%	n	%
Yes										
No										
Not Evaluated										
Missing										
Total										

**TABLE 17.6 SHIFT CHANGES OF ALLERGIC RHINITIS****TABLE 17.7 SHIFT CHANGES OF BRONCHIECTASIS****TABLE 17.8 SHIFT CHANGES OF LUNG DISEASES DUE TO EXTERNAL AGENTS**

Shame shells as 17.5

**TABLE 17.9 SHIFT TABLE OF GOLD GROUP**

	Baseline		3 Months						Total	
	A	B	C	D	Missing					
	n	%	n	%	n	%	n	%	n	%
Gold group										
A										
B										
C										
D										
Missing										
Total										

**TABLE17.10 LISING OF OUTLIERS**

Patient Code	Variable	Value	Visit	Procedure Taken*

\*If applicable

**TABLE 17.11.1 OVERVIEW OF ADVERSE EVENTS**

	n (%)
Subjects treated	
Subjects with at least one:	
AE	
ADR	
Serious AE	
Serious AE leading to drug discontinuation	
Serious AE Leading to Death	
Number of pregnant patients with at least one AE	

**TABLE 17.11.2 OVERVIEW OF ADVERSE EVENTS RELATED TO COVID-19**

	n (%)
Subjects treated	
Subjects with at least one:	
AE related to COVID-19	
Serious AE related to COVID-19	
Serious AE leading to drug discontinuation related to COVID-19	
Serious AE Leading to Death related to COVID-19	

